Covariates will be identified in data from claims and electronic health records (where available, as not all data research partners will have access to electronic health records) using administrative health plan enrollee data or codes for diagnoses (with procedures or

medications, as appropriate). The following potential variables will be identified in relation to the index date (i.e., cohort entry date), to be included in descriptive analysis and to be considered as potential confounders in analysis of general safety events.

- Demographics (on the index date, unless otherwise noted): age, sex, geographic region (using the latest information available as of the index date), and race/ethnicity (if feasible)
- Date of Pfizer-BioNTech original monovalent COVID-19 Vaccine (categorized as appropriate, e.g., by year or month) and dose of vaccine received (e.g., 1, 2, 3)
- Medical history:
 - Comorbidities (in the 12 months before, not including the index date): history of anaphylaxis, history of allergies, diabetes (type 1, type 2, gestational diabetes in current pregnancy), hypertension, cardiovascular disease, cerebrovascular diseases, chronic respiratory disease, chronic kidney disease, chronic liver disease, cancer, epilepsy, autoimmune disorders, influenza and other respiratory infections (including COVID-19), immunocompromising conditions, gastrointestinal infections, and obesity (capture anticipated to be incomplete)
 - Pregnancy status (on the index date)
 - Medications and non-COVID-19 vaccinations (in the 12 months before or on the index date), including vaccines administered concomitantly with Pfizer-BioNTech original monovalent COVID-19 Vaccine
 - Healthcare utilization (in the 12 months before or on the index date): any healthcare encounter (including telehealth encounters, if feasible); hospitalizations; emergency department visits; cancer screening(s); skilled nursing facility, nursing home, or extended care facility stay; other preventive healthcare services, as appropriate; and COVID-19 tests

For comparative analyses of pregnancy safety outcomes among pregnant women, the following potential confounders and descriptive variables will be identified in relation to the index date.

- Demographics (on the index date, unless otherwise noted): maternal age, geographic region (using the latest available information on index date), race/ethnicity (if feasible)
- Medical history:

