8.3.3.1. Potential confounding variables

The following variables will be used to describe the overall study population, immunocompromised individuals, individuals with a history of COVID-19, and pregnant women and will be considered as potential confounding variables to be included in propensity score models for analysis of general safety events.

- Demographics will be evaluated at the index date for each individual, unless otherwise noted
- Age: Individuals of all ages will be included in the study; for descriptive analyses, age categories will be 0-4, 5-11, 12-15, 16-20, 21-29, 30-49, 50-64, 65-80, and greater than 80 years
- Sex
- Geographic region (zip code where available, state or census region; evaluated using the latest information available on the index date)
- Race/ethnicity: Data on race/ethnicity are anticipated to be incomplete, and the feasibility of including this variable in the analyses will be assessed before study start
- Date of Pfizer-BioNTech original monovalent COVID-19 Vaccine (categorized as appropriate, e.g., by year or month)
- Dose of vaccine received (e.g., 1, 2, 3)
- Comorbidities, identified in the 12 months before the index date (unless otherwise noted) in claims or electronic health records using diagnosis codes (with procedure and/or pharmacy dispensing codes as appropriate)
 - History of anaphylaxis (not including the index date)
 - History of allergies
 - Diabetes mellitus (type 1, type 2, or gestational diabetes in current pregnancy)
 - Hypertension

PFIZER CONFIDENTIAL

CT24-WI-GL02-RF02 3.0 Non-Interventional Study Protocol Template For Secondary Data Collection Study 20-May-2021 Page 71 of 120

- Cardiovascular disease
- Cerebrovascular disease
- Chronic respiratory disease
- Chronic kidney disease
- Chronic liver disease
- Cancer
- Epilepsy
- Autoimmune disorders
- Influenza and other respiratory infections (including COVID-19)
- Gastrointestinal infections
- Immunocompromising conditions, including the following (to be defined in more detail in the SAP):
 - Immunodeficiencies
 - Immunosuppressant medication use
 - Human immunodeficiency virus and other immunosuppressing conditions
 - Receipt of organ or bone marrow transplant
- Obesity (to be identified with proxies using diagnosis and procedure codes; capture anticipated to be incomplete)
- Preeclampsia/eclampsia (captured only in subgroup analysis of pregnant women)

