- Pregnancy status (on the index date), identified using an algorithm as described in Section 8.2.3
- Medications in the 12 months before and including the index date, identified in data from claims or electronic health records via procedure and/or pharmacy dispensing codes
 - Analgesics

PFIZER CONFIDENTIAL

CT24-WI-GL02-RF02 3.0 Non-Interventional Study Protocol Template For Secondary Data Collection Study 20-May-2021 Page 72 of 120

- Antibiotics
- Antiviral medications
- Corticosteroids
- Nonsteroidal anti-inflammatory drugs
- Psychotropics
- Statins
- Novel oral anticoagulants
- Warfarin
- Non-COVID-19 vaccinations (including those administered concomitantly with Pfizer-BioNTech original monovalent COVID-19 Vaccine) in the 12 months before or on the index date, identified in data from claims or electronic health records with procedure and/or pharmacy dispensing codes
 - Influenza
 - Pneumococcal disease
 - Diphtheria, tetanus, and pertussis
 - Polio
 - Measles, mumps, and rubella
 - Haemophilus influenzae type b
 - Hepatitis B virus
 - Human papillomavirus
 - Meningitis
 - Rotavirus
 - Varicella
 - Herpes zoster

CT24-WI-GL02-RF02 3.0 Non-Interventional Study Protocol Template For Secondary Data Collection Study 20-May-2021 Page 73 of 120

- Healthcare utilization (including telehealth encounters, if feasible) in the 12 months before or on the index date
 - Any healthcare encounter
 - Hospitalizations
 - Emergency department visits
 - Skilled nursing facility, nursing home, or extended care facility stay
 - Cancer screening(s)
 - Other preventive healthcare services, as appropriate
 - COVID-19 tests

The following variables will be used to describe the population of pregnant women and will be considered as potential confounders to be included in propensity score models for analysis of pregnancy safety outcomes. Except where noted, only information up to and including the index date will be used to identify potential confounders.

- Demographics: maternal age (on the index date), geographic region (using the latest information available as of the index date), race/ethnicity (if feasible, on the index date)
- Comorbidities, identified in the 12 months before the index date in claims or electronic health records using diagnosis codes (with procedure and/or pharmacy dispensing codes as appropriate).
 - Diabetes mellitus (type 1, type 2)
 - Hypertension
 - Connective tissue disorders
 - Thyroid disorders
 - Heart disease
 - Epilepsy and mood disorders

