 - Asthma
 - Liver disease

PFIZER CONFIDENTIAL

CT24-WI-GL02-RF02 3.0 Non-Interventional Study Protocol Template For Secondary Data Collection Study 20-May-2021 Page 74 of 120

- Kidney disease
- Cancer
- Obesity, identified in the 12 months before the index date, with proxies based on diagnosis and procedure codes (capture anticipated to be incomplete since documentation via diagnosis or procedure codes is not routinely done in claims data)
- Alcohol use, identified in the 12 months before the index date, with proxies based on diagnosis and procedure codes (capture anticipated to be incomplete)
- Smoking, identified in the 12 months before the index date, with proxies based on diagnosis and procedure codes (capture anticipated to be incomplete)
- Multiple pregnancy, identified during pregnancy via diagnosis codes. Information recorded after the index date will be used to identify potential confounders
- Gestational diabetes, identified during pregnancy via diagnosis codes
- Preeclampsia/eclampsia, identified during pregnancy via diagnosis codes
- Gestational hypertension
- TORCH infections (toxoplasmosis, other [syphilis, varicella-zoster, parvovirus B19], rubella, cytomegalovirus, and herpes infections), identified during pregnancy via diagnosis codes
- Teratogenic medications from 28 days before pregnancy up to and including the end of pregnancy, identified via pharmacy dispensing and procedure codes
- Vaccinations other than COVID-19 vaccinations (including those administered concomitantly with Pfizer-BioNTech original monovalent COVID-19 Vaccine) from 28 days before pregnancy up to and including the end of pregnancy, identified via pharmacy dispensing and procedure codes

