8.3.3.2. Variables for identifying subcohorts

Three subcohorts will be identified from the general population cohort in which descriptive and comparative analyses of general safety events will be conducted: individuals with immunocompromising conditions, pregnant women, and individuals with a history of COVID-19. Comparative safety analyses of pregnancy safety outcomes will also be conducted in pregnant women. These 3 subcohorts will be identified as follows:

• Immunocompromising conditions will be identified using diagnosis, procedure, and medication dispensing codes in the 12 months before the index date for

CT24-WI-GL02-RF02 3.0 Non-Interventional Study Protocol Template For Secondary Data Collection Study 20-May-2021 Page 75 of 120 immunodeficiencies, immunosuppressant medication use, human immunodeficiency virus and other immunosuppressing conditions, and receipt of organ or bone marrow transplant.

- Pregnancy status will be identified using an algorithm as described in Section 8.2.3.
- History of COVID-19 (in all available data) will be identified in data from claims or electronic health records via ICD-10-CM (International Classification of Diseases, 10th Revision, Clinical Modification) diagnosis codes for COVID-19 (U07.1), personal history of COVID-19 (Z86.16), or pneumonia due to COVID-19 (J12.82). If feasible, a positive laboratory test result for SARS-CoV-2 will be incorporated into the definition.

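### The confounder list for pregnancy and birth outcomes leaves out prior COVID-19, COVID-19 tests, immunocompromise and healthcare use, which the protocol lists for the same women in other analyses

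*Protocol*

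**What the plan says.** Section 8.3.3.1 of the protocol sets out two groups of variables, each tied to a class of outcome.

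- The first describes all study groups, including "pregnant women and will be considered as potential confounding variables to be included in propensity score models for analysis of general safety events". It contains "Influenza and other respiratory infections (including COVID-19", a block of immunocompromising conditions, and "Healthcare utilization (including telehealth encounters, if feasible) in the 12 months before or on the index date". That last block covers any encounter, hospitalizations, emergency department visits, preventive services and COVID-19 tests.
- The second is introduced as variables that "will be considered as potential confounders to be included in propensity score models for analysis of pregnancy safety outcomes". It holds demographics, chronic comorbidities, obesity, alcohol, smoking, multiple pregnancy, gestational diabetes, preeclampsia/eclampsia, gestational hypertension, teratogenic medications and non-COVID-19 vaccinations. Its one infection item is "TORCH infections (toxoplasmosis, other [syphilis, varicella-zoster, parvovirus B19], rubella, cytomegalovirus, and herpes infections), identified during pregnancy via diagnosis codes".

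The abstract makes the same split. For pregnancy outcomes it says that "the following potential confounders and descriptive variables will be identified in relation to the index date", and the items that follow again lack the four named above.

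Section 8.7.2.3.2.1 step b describes the propensity model for pregnant women. It takes its covariates from Section 8.3.3 as a whole, without saying which list applies to which outcome.

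**The concern.** Vaccinated and unvaccinated pregnant women may differ in prior COVID-19 and in how much care they use. Both could plausibly be related to pregnancy outcomes or to whether those outcomes are recorded. The protocol itself treats these variables as relevant: it adjusts for them in general safety events, says in Section 8.1 that care-seeking and utilization may affect outcome ascertainment, and says in Section 8.9 that spontaneous abortion will be incompletely captured. It gives no reason for adjusting for them when a pregnant woman is studied for a general safety event but not when she is studied for stillbirth or preterm birth.

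At stake are the comparisons for spontaneous abortion, stillbirth, preterm birth, small size for gestational age and major malformations. The last two are the subject of primary objective 4.

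**Working it through.** The protocol gives no figure on this point, and Table 9 contains no pregnancy or birth outcome, so there is nothing to reproduce. The check is a comparison of the text, followed by an illustration on assumed inputs.

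**Step 1: the two lists side by side (Section 8.3.3.1)**

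| Item | General safety events (includes pregnant women) | Pregnancy safety outcomes |
|---|---|---|
| COVID-19 or other respiratory infection | listed | absent |
| COVID-19 tests | listed | absent |
| Immunocompromising conditions | listed | absent as such |
| Hospitalizations, emergency visits, preventive care | listed | absent |
| Non-COVID-19 vaccinations | listed | listed |

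**Step 2: can the missing items be measured?** Yes. Section 8.3.3.2 states that "History of COVID-19 (in all available data) will be identified in data from claims or electronic health records", with named diagnosis codes. Section 8.4 shows encounter type in the common data model.

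**Step 3: does another part of the design cover the gap?**

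- Matching of pregnant women (Sections 8.7.2.3.2.1 and 8.7.2.3.2.3) uses pregnancy start, state or region, and maternal age. None of these is an individual measure of infection or care use.
- Section 8.7.3.2 excludes pregnancy safety outcomes from the self-controlled risk interval design.
- The historical comparator analysis (Section 8.7.3.3) is conditional on feasibility, is aimed at exposure misclassification, and names only maternal age and pregnancy start for matching.

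**Step 4: how large could the bias be?** Every input here is an assumption; none comes from the protocol. With a true ratio of 1, p1 and p0 the prevalence of prior COVID-19 in vaccinated and unvaccinated women, and RR the risk ratio of infection on the outcome:

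bias factor = [1 + p1(RR - 1)] / [1 + p0(RR - 1)]

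| p1 v p0 | RR = 1.5 | RR = 3 |
|---|---|---|
| 2% v 5% | 1.010/1.025 = 0.985 | 1.04/1.10 = 0.945 |
| 3% v 8% | 1.015/1.040 = 0.976 | 1.06/1.16 = 0.914 |
| 3% v 12% | 1.015/1.060 = 0.958 | 1.06/1.24 = 0.855 |

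With the imbalance reversed, at 15% v 10%:

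- RR 1.3: 1.045/1.030 = 1.015
- RR 2.0: 1.15/1.10 = 1.045

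For high care use treated as protective, at 70-80% of vaccinated v 50-60% of unvaccinated women and a risk ratio of 0.6-0.9, the same formula gives:

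- mildest case: (1 - 0.7 × 0.1)/(1 - 0.6 × 0.1) = 0.93/0.94 = 0.989
- strongest case: (1 - 0.8 × 0.4)/(1 - 0.5 × 0.4) = 0.68/0.80 = 0.85

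**Step 5: what does the index date allow?** For spontaneous abortion, stillbirth and preterm birth, the index is the vaccination date or the matched gestational age (Table 4). Infection earlier in the pregnancy can therefore be a baseline covariate. For small size for gestational age and malformations, the index is estimated pregnancy start (Table 6). No infection in the current pregnancy can precede it.

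**The case against.** The strongest reply is that step b of Section 8.7.2.3.2.1 refers to Section 8.3.3 in full. That would bring in both lists and the COVID-19 history of Section 8.3.3.2. The same section describes one process for general safety events and pregnancy outcomes together and nowhere says that the model switches lists. This stands as an ambiguity. It does not settle the matter, because Section 8.3.3.1 assigns each list to an outcome class and the abstract repeats the assignment.

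It can also be said that the variables are only to be considered, and that propensity score details are left to the SAP. It is true that the lists are not declared closed. However, what Section 8.3.3 defers is the algorithms and code lists for each covariate, not the choice of covariates.

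Part of the gap is already covered. The pregnancy list includes "Vaccinations other than COVID-19 vaccinations (including those administered concomitantly with Pfizer-BioNTech original monovalent COVID-19 Vaccine", a partial marker of care-seeking, and cancer and connective tissue disorders overlap somewhat with immunocompromise. Matching on pregnancy start and region aligns calendar time and local epidemic conditions. Continuous enrollment to the end of pregnancy limits gross differences in observability. These measures may shrink an imbalance, but they do not measure prior infection or care use in the individual woman.

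A reader might go further and infer that the estimates are certain to be confounded, or that they will be pulled below 1 and hide harm. The documents support neither. They give no prevalence of infection by vaccination status and no effect of infection on any outcome, and the direction reverses if infection is commoner in vaccinated women. Nor can an imbalance in COVID-19 earlier in pregnancy at index be invoked for small size for gestational age or malformations, given their index date.

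**Conclusion.** The omission is real, and it appears in both Section 8.3.3.1 and the abstract. The text is also inconsistent about which list feeds the propensity score in pregnant women. Followed as written in Section 8.3.3.1, the plan leaves pregnancy and birth outcome estimates at avoidable risk of confounding from prior COVID-19, immunocompromise and care use.

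This is a risk, not a demonstrated bias. For COVID-19 alone, the assumed prevalences of 2-3% v 5-12% and risk ratios of 1.5-3 give a factor between 0.985 and 0.855, and the sign depends on the imbalance. The care-use range of 0.989 to 0.85 is likewise conditional on its inputs. The change is worth making before the analysis because the variables are already planned for the same women and nothing else in the design substitutes for them.

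**What to change.** Add four items to the pregnancy-outcome list in Section 8.3.3.1 and in the abstract: prior COVID-19, COVID-19 tests, immunocompromising conditions and healthcare utilization. Use the definitions already planned for general safety events, restricted to information before the index date. The present utilization definition includes the index date itself, so that part needs trimming.

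Reword step b of Section 8.7.2.3.2.1 so that it names the list to be used for each outcome class. Sections 8.7.2.3.2.2 and 8.7.2.3.2.3 refer back to it and will follow.

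State the scope by outcome:

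- **Spontaneous abortion, stillbirth and preterm birth:** include COVID-19 earlier in the pregnancy as well as before it.
- **Small size for gestational age and major malformations:** include pre-pregnancy history only, and say plainly that infection during pregnancy before vaccination remains uncontrolled.

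The cost is a few lines of text and minor programming to rebuild the covariates at the pregnancy-start index. No new data source is needed.

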8.3.3.2. Variables for identifying subcohorts

Three subcohorts will be identified from the general population cohort in which descriptive and comparative analyses of general safety events will be conducted: individuals with immunocompromising conditions, pregnant women, and individuals with a history of COVID-19. Comparative safety analyses of pregnancy safety outcomes will also be conducted in pregnant women. These 3 subcohorts will be identified as follows:

• Immunocompromising conditions will be identified using diagnosis, procedure, and medication dispensing codes in the 12 months before the index date for

CT24-WI-GL02-RF02 3.0 Non-Interventional Study Protocol Template For Secondary Data Collection Study 20-May-2021 Page 75 of 120 immunodeficiencies, immunosuppressant medication use, human immunodeficiency virus and other immunosuppressing conditions, and receipt of organ or bone marrow transplant.

- Pregnancy status will be identified using an algorithm as described in Section 8.2.3.
- History of COVID-19 (in all available data) will be identified in data from claims or electronic health records via ICD-10-CM (International Classification of Diseases, 10th Revision, Clinical Modification) diagnosis codes for COVID-19 (U07.1), personal history of COVID-19 (Z86.16), or pneumonia due to COVID-19 (J12.82). If feasible, a positive laboratory test result for SARS-CoV-2 will be incorporated into the definition.

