Dose 3 unexposed	 As of the index date, receipt of 2 doses in a primary series of Pfizer-BioNTech original monovalent COVID-19 Vaccine, with no receipt of a third dose of any COVID-19 vaccine Individually matched to individuals in the dose 3 exposed cohort (in at least a ratio of 1:1) on time-specific propensity score (which is described in Section 8.7.2.3.1), age, sex, state of residence (if feasible, or broader geographic region if not feasible), calendar time, and time since receipt of dose 2 	Randomly selected date in a period within close temporal proximity to the date of receipt of dose 3 in corresponding exposed individuals (e.g., within the same calendar month)	Record of any COVID- 19 vaccine other than Pfizer-BioNTech original monovalent COVID-19 Vaccine before the index date

COVID-19 = coronavirus disease 2019.

Individuals who receive 3 doses of the Pfizer-BioNTech original monovalent COVID-19 Vaccine can contribute non-overlapping person-time to both the dose 3 exposed and dose 3 unexposed cohorts. Individuals in the dose 3 unexposed cohort may also contribute persontime to the dose 3 exposed cohort if they subsequently receive a third dose of the Pfizer-BioNTech original monovalent COVID-19 Vaccine more than 2 months after the second dose. Conversely, individuals in the dose 3 cohort may be eligible for inclusion in the dose 3 unexposed cohort before they receive a third dose of Pfizer-BioNTech original monovalent COVID-19 Vaccine.

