8.7.2.3. Methods for addressing confounding

8.7.2.3.1. General population, immunocompromised individuals, and individuals with a history of COVID-19

Analysis of nonpregnant populations will use matching on age, sex, state (if feasible, or broader geographic region if not feasible), and time–specific propensity scores within the data from each data research partner to account for confounding. The propensity score is the predicted probability of an individual being in the exposed cohort rather than in the corresponding unexposed cohort, given a set of observed covariates. Additionally, analysis of third doses received more than 2 months after the second dose will also match on time since receipt of the second dose.

8.7.2.3.1.1. Analysis of general safety events following primary series

Among the general population, immunocompromised individuals, and individuals with a history of COVID-19, the risk of general safety events will be compared among individuals who have received at least the first dose in a primary series of Pfizer-BioNTech original monovalent COVID-19 Vaccine versus those among individuals who have not received any COVID-19 vaccine during a concurrent time. In individuals aged 6 months through 4 years, these analyses will include doses 1, 2, and 3. Details for handling the timing between individual doses in this age group will be described in the SAP. In individuals aged 5 years and older, these analyses will include dose 1 and dose 2, as well as dose 3 if a third dose is received within 2 months of the second dose.

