Estimation of propensity scores will be performed for the dose 1, 2, and 3 (if applicable) cohorts combined. However, matching of exposed to unexposed individuals will be done separately for the dose 1 exposed cohort, the dose 2 exposed cohort, and the dose 3 exposed cohort within narrow time periods to account for changing predictors of vaccination over time, seasonality of circulating infections, and changes in healthcare utilization over time. Matching will occur by age and state (if feasible, or broader geographic region if not feasible) within each time period and dose number. The matching and propensity score estimation process will be done first for the general population and then will be repeated separately for immunocompromised individuals and for individuals with a history of COVID-19. Propensity score estimation will be conducted within each data research partner. The steps for propensity score modeling and matching are as follows.

a. Within each data research partner, the study period will be divided into 1-month intervals of calendar time ("time intervals"). All individuals who received a vaccine dose— whether dose 1, dose 2, or dose 3—during the considered month would contribute vaccinated index dates during the time interval; if an individual received more than 1 dose during a calendar month, all eligible index dates will be included as independent observations in the propensity score model. All individuals with at least 1 unexposed

PFIZER CONFIDENTIAL

CT24-WI-GL02-RF02 3.0 Non-Interventional Study Protocol Template For Secondary Data Collection Study 20-May-2021 Page 92 of 120 person-day in the time interval will have an unvaccinated index date randomly assigned during all unexposed person-time within the time interval. In this context, "unexposed person-day" refers to a day in which the individual has no record of COVID-19 vaccine on or before that day.

- b. Within each time interval, the propensity to be vaccinated will be estimated among all individuals with index dates within the time interval using logistic regression. The dependent variable for the logistic regression model will be vaccination status, and the independent variables will be baseline covariates (i.e., individual characteristics as described in Section 8.3.3). The model will combine dose 1, dose 2, and dose 3 index dates, which assumes that the factors influencing an individual's likelihood of being vaccinated does not change between dose 1, dose 2, and dose 3.

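### The history-of-COVID-19 subcohort sets no minimum time since infection and neither matches nor adjusts on it, so the subgroup RR can be biased, probably downward, for outcomes that acute COVID-19 raises

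*Protocol*

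**What the plan says.** **Entry.** Section 8.3.3.2 states: "History of COVID-19 (in all available data) will be identified in data from claims or electronic health records via ICD-10-CM", and the qualifying codes are "diagnosis codes for COVID-19 (U07.1), personal history of COVID-19 (Z86.16), or pneumonia due to COVID-19 (J12.82". One code is enough. A positive test may be added if feasible. No lag before the index date is given.

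**Matching.** For non-pregnant populations, Section 8.7.2.3.1 specifies "matching on age, sex, state (if feasible, or broader geographic region if not feasible), and time–specific propensity scores". The score is estimated by calendar month and data partner, and the process is repeated within this subcohort. Late third-dose analyses "will also match on time since receipt of the second dose"; Table 2 (Section 8.2.2.2) likewise lists "calendar time, and time since receipt of dose 2". No list includes time since infection.

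**Covariates.** Section 8.3.3.1 has the item "Influenza and other respiratory infections (including COVID-19", with a 12-month look-back. It also lists hospitalizations, emergency visits, COVID-19 tests, antivirals, corticosteroids and anticoagulants over 12 months. No recency category is stated for any of them.

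**Index dates.** For exposed persons the index date is the vaccination date (Table 1). In Section 8.7.2.3.1.1 an unvaccinated person "will have an unvaccinated index date randomly assigned during all unexposed person-time within the time interval".

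**Outcomes.** In Table 8 the windows start on day 1 and run to day 28 for ARDS, pulmonary embolism, deep vein thrombosis, stroke and myocardial infarction, to day 42 for multisystem inflammatory syndrome, and to day 21 for myocarditis/pericarditis.

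**The concern.** U07.1 and J12.82 denote COVID-19 and COVID-19 pneumonia; personal history has its own code, Z86.16. Without a lag, someone coded with current disease shortly before the index date counts as having a history. A random unvaccinated day can fall in or soon after an acute episode. A vaccination day is one on which the person presented for a vaccine, and Section 8.7.3.2 itself recognizes healthy-vaccinee effects.

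If comparators are indexed soon after infection more often than vaccinees, and acute COVID-19 raises the outcome, infection-related events inflate the reference rate. A true excess could be hidden, or the vaccine could look protective. The outcome washout (Section 8.7.2) does not prevent this, because it removes people who already had the outcome, not people recently infected.

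The RR in this subgroup falls under primary objectives 1 to 3 (Section 7).

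**Working it through.** **The plan's own figure.** The protocol gives no size or precision figure for this subcohort. Its overall-population example in Section 8.5 reproduces:

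- Comparator events: 5,000,000 × 2 doses × (21/365.25) × 10/100,000 = 57.5. Exposed events: 1.4 × 57.5 = 80.5.
- SE = √(1/57.5 + 1/80.5) = 0.173.
- Φ[(ln 2.5 − ln 1.4)/0.173 − 1.96] = 0.919, against the stated 92%.

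That calculation is not in dispute and does not bear on this point.

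**Which part of the plan could balance recency?**

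- Subcohort entry: all available data, so last week and two years ago both qualify.
- Matching list: calendar month of the index date is controlled; the date of infection is not.
- Respiratory-infection covariate: as listed, it separates at most within 12 months from earlier. It does not separate last week from 11 months ago.
- Utilization, test and drug covariates: proxies for a recent episode, but also over 12 months.

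**Illustration of size.** All inputs are assumptions; none comes from the protocol.

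- q0 = share of comparators indexed within 28 days of infection. With dates spread evenly over one year, q0 = 28/365 = 0.0767.
- q1 = the same share among vaccinees, set to 0.
- k = event rate ratio during the 28 days after infection, against later.
- s = average fraction of the risk window that falls inside those 28 days, for a person indexed in them. Follow-up starts after the index date, so a person indexed on day 20 has only about 8 raised days. The mean is 14 days, giving s = 14/28 = 1/2 for a 28-day window and 14/42 = 1/3 for a 42-day window.

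Observed RR = true RR × [1 + q1·s·(k − 1)] / [1 + q0·s·(k − 1)].

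For a true RR of 1.0:

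| k | 28-day window | 42-day window |
|---|---|---|
| 3 | 1/(1 + 0.0767 × 0.5 × 2) = 0.93 | 1/(1 + 0.0767 × 0.333 × 2) = 0.95 |
| 5 | 1/(1 + 0.0767 × 0.5 × 4) = 0.87 | 1/(1 + 0.0767 × 0.333 × 4) = 0.91 |
| 10 | 1/(1 + 0.0767 × 0.5 × 9) = 0.74 | 1/(1 + 0.0767 × 0.333 × 9) = 0.81 |

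**Range (28-day window, k = 3, 5, 10).**

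- Dates spread over six months, q0 = 28/180 = 0.156: 0.87, 0.76, 0.59.
- Dates spread over two years, q0 = 28/730 = 0.038: 0.96, 0.93, 0.85.
- q0 = 1% and k = 2: 1/(1 + 0.01 × 0.5 × 1) = 0.995, which is negligible.
- q1 = q0: the ratio is 1, so there is no bias. This is what balancing on recency aims for.

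**When a true RR of 1.4 would read 1.0.** This needs q0·s·(k − 1) = 0.40. With a 28-day window and dates over one year, k = 1 + 0.40/0.0384 ≈ 11.4; over six months, k = 1 + 0.40/0.0778 ≈ 6.1.

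**The case against.** The strongest replies, and what remains of each:

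- **The groups are not shown to differ.** The protocol gives no infection-to-vaccination timing and no share of recent infections in either group. This stands. A reader might infer that acutely ill comparators are set against recovered vaccinees and that the RR is pulled down. The document supports only that recency is uncontrolled and may differ. Direction and size also depend on the outcome.
- **Entry from the first day and a yes/no covariate are not in the text.** This also stands. Section 8.3.3.2 does not say whether a code on the index date counts, and Section 8.3.3 leaves covariate algorithms to the SAP.
- **Other covariates help.** Hospitalizations, tests, antivirals and the like are candidates for a score re-estimated within this subcohort each month. They give partial, unquantified control.
- **A self-controlled analysis is planned.** Section 8.7.3.2 names this subcohort and covers acute-onset outcomes with windows up to 42 days. It uses vaccinated people only, with post-vaccination control intervals, so comparator illness cannot enter. It is a real check, but a sensitivity analysis. It does not correct the cohort RR, unless incomplete exposure data lead to it becoming the primary design.
- **The SAP may settle it.** Eligibility and matching details are deferred, and a lag could be set there. But the protocol itself fixes the look-back and the list of matching variables, and names time since dose 2 at that level.
- **Time since dose 2 is a different matter.** The protocol does not present it as a remedy for this problem. It shows only that matching on elapsed time is already part of the design.

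**Conclusion.** The design gap is certain from the text: no minimum interval since infection, and no matching or stated covariate that captures it, in a subgroup of the primary objectives. That this can bias the cohort RR follows directly. That the bias is probably downward, for outcomes acute COVID-19 raises, is a reasoned inference. It requires more recent infection among comparators than among vaccinees and k above 1; the reverse imbalance would reverse it.

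The size is unknown. Under the stated one-year assumptions a null RR reads 0.74 to 0.93 (28-day window) or 0.81 to 0.95 (42-day window) for k from 10 down to 3, and it can be negligible. A reader might apply k to the whole follow-up of everyone indexed within 28 days of infection, which gives 1/(1 + 0.0767 × (k − 1)) = 0.87, 0.77 and 0.59. That overstates the effect under these assumptions, because on average only half of a 28-day window, or a third of a 42-day window, is raised.

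This should be changed before the comparative analysis of the subgroup, with high confidence in the gap and low confidence in its magnitude.

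**What to change.** In the history-of-COVID-19 analyses (Sections 8.2.2 and 8.7.2.3.1):

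1. Match on, or include in the propensity score, bands of time since the most recent acute COVID-19 code (U07.1 or J12.82, or a positive test where available), for example 0–30, 31–90, 91–180 and more than 180 days. Give persons with only Z86.16 a separate category, since that code does not date the infection.
2. Add a sensitivity analysis that excludes, in both cohorts, anyone whose last acute code falls within the length of the outcome's risk window before the index date.
3. State whether a code on the index date counts toward entry.
4. Use the same recency bands as a propensity score covariate in the general population.

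The cost is protocol and SAP wording plus one derived variable; diagnosis dates are already in the common data model (Section 8.4). Some exposed persons in sparse bands may go unmatched, which costs precision, and Z86.16-only persons cannot be placed in a dated band.
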